10.1.2 Total Exposure to Pimavanserin Across the Double-blind and Open-label Periods

For subjects who received pimavanserin in the antecedent study, the total duration of exposure (in days) to pimavanserin will be calculated as the sum of the exposure durations in the double-blind and open-label periods:

$$[(\text{date of last double-blind dose}) - (\text{date of first double-blind dose}) + 1] + [(\text{date of last open-label dose}) - (\text{date of first open-label dose}) + 1].$$

For subjects who received placebo in the antecedent studies, the total duration of exposure to pimavanserin across the double-blind and open-label periods will be the same as the values calculated for the open-label study period alone.

Duration of total exposure to pimavanserin will be summarized as both continuous and categorical variables. For categorical presentation, the number and percentage of subjects in each of the following categories will be presented: <2 weeks (1 to 13 days), 2 to <6 weeks (14 to 41 days), 6 to <12 weeks (42 to 83 days), 12 to <20 weeks (84 to 139 days), 20 to <28 weeks (140 to 195 days), 28 to <36 weeks (196 to 251 days), 36 to <44 weeks (252 to 307 days), 44 to <52 weeks (308 to 363 days), 52 to <60 weeks (364 to 419 days), 60 to <68 weeks (420 to 475 days), 68 to <78 weeks (476 to 545 days), and \geq 78 weeks (546 days or longer).

10.2 Measurement of Treatment Compliance

Study drug dosing compliance (in percentage) during the open-label treatment period for a subject is defined as the total number of capsules actually taken divided by the number of capsules expected to be taken and then multiplied by 100. The total number of capsules actually taken is calculated by the total number of capsules dispensed minus the total number of capsules returned. The number of capsules expected to be taken is calculated as the duration of exposure (days) \times 1 (number of capsules taken per day).

Compliance will be summarized as both continuous and categorical variables. For categorical presentation, the number and percentage of subjects in each of the following categories will be presented: <80%, 80 to 120%, and >120%.

Listings of study drug accountability will be provided separately.

11 CONCOMITANT AND POST-TREATMENT MEDICATION

Concomitant medication is defined as any medication with a start date prior to the date of the open-label first dose and continuing after the open-label first dose date or with a start date between the open-label first dose date and open-label last dose date, inclusive. Any medication with a start date after the date of the last dose of open-label study drug will be considered as post-treatment medication. Concomitant and post-treatment medications will be summarized separately.

Medications will be coded using WHO Drug Dictionary 2021 March or newer version. The number and percentage of subjects taking each drug class (ATC Level 3) and medication preferred term will be tabulated for the Safety Analysis Set. Multiple medication usage by a subject in the same category will be counted only once.

Relationship to COVID-19 will be assessed for selected medications as detailed in the GSD and provided in a listing. Additional summaries of relationship to COVID-19 may be provided.

Listings of the concomitant and post-treatment medications will be provided.

12 EFFICACY ANALYSIS CONSIDERATIONS

All efficacy analyses will be performed using the Safety Analysis Set. No hypothesis testing is planned. Descriptive summaries of efficacy endpoints will be provided.

12.1 Efficacy Variables

Secondary Efficacy Endpoint

The secondary efficacy endpoint is defined as follows:

- Proportion of subjects who have at least 25% reduction from the antecedent study Baseline in the ABC-I subscale score and a CGI-I of irritability score of 1 (very much improved) or 2 (much improved) compared to the antecedent study baseline status at Week 52.

Exploratory Efficacy Endpoints

- Change from Baseline at Week 52 in the caregiver-rated ABC subscale scores
 - Irritability
 - Stereotypic behavior

- Lethargy
- Hyperactivity
- Inappropriate speech
- Change from Baseline at Week 52 in the CGI-S of irritability score
- CGI-I of irritability score from the antecedent study Baseline at Week 52
- Proportion of subjects who have at least 25% reduction from the antecedent study Baseline in the ABC-I subscale score (ABC-I responders) at Week 52
- Proportion of subjects who have CGI-I of irritability score of 1 (very much improved) or 2 (much improved) compared to the antecedent study baseline status (CGI-I of irritability responders) at Week 52

12.2 Adjustment for Covariates

Not applicable.

12.3 Handling of Missing Data

Any derived scores (i.e., total, domain, or subscale scores) that are missing after the imputation of individual missing items (if any) will not be imputed.

12.4 Multiple Comparisons / Multiplicity

No hypothesis testing is planned.

12.5 Examination of Subgroups

Summaries of the change from Baseline in the ABC-I subscale scores will be presented by subgroups below:

- age group (5 through 12 years old or 13 through 17 years old) as stratified in antecedent study
- sex (male or female)
- primary race (white or non-white)
- IQ from antecedent study (<70 or ≥ 70)
- region (US. or rest of world) as stratified in antecedent study
- severity of ABC-I at antecedent study entry (<25 or ≥ 25)
- severity of ABC-Lethargy at antecedent study entry (ABC-L) (<20 or ≥ 20)

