**“WARNING: INCREASED MORTALITY IN ELDERLY PATIENTS WITH DEMENTIA-RELATED PSYCHOSIS”**

The increased mortality warning in elderly patients with dementia-related psychosis is based on information regarding antipsychotic drugs in general, rather than specific pimavanserin data.

The Warnings and Precautions section of the Prescribing Information for pimavanserin also includes information about QT interval on ECG (QT) interval prolongation. Pimavanserin prolongs the QT interval. The use of pimavanserin should be avoided in patients with known QT prolongation or in combination with other drugs known to prolong QT interval including Class 1A antiarrhythmics (e.g., quinidine, procainamide) or Class 3 antiarrhythmics (e.g., amiodarone, sotalol), certain antipsychotic medications (e.g., ziprasidone, chlorpromazine, thioridazine), and certain antibiotics (e.g., gatifloxacin, moxifloxacin). Pimavanserin should also be avoided in patients with a history of cardiac arrhythmias, as well as other circumstances that may increase the risk of the occurrence of torsade de pointes and/or sudden death, including

symptomatic bradycardia, hypokalemia or hypomagnesemia, and the presence of congenital prolongation of the QT interval.

NUPLAZID is contraindicated in patients with a history of a hypersensitivity reaction to pimavanserin or any of its components. Rash, urticaria, reactions consistent with angioedema (e.g., tongue swelling, circumoral edema, throat tightness, and dyspnea) have been reported. In addition, adverse reactions of somnolence, falls, agitation, and aggression have been reported during postapproval use of NUPLAZID.

Pimavanserin has not yet been studied as monotherapy in children and adolescents therefore no data are available on specific risks in this population. In adolescents treated with pimavanserin in combination with other psychotropics, pimavanserin dose-related QTc prolongation, and a trend for higher exposure with decreasing age and decreasing body weight, have been observed.

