3 STUDY DESIGN

3.1 General Study Design

This study will be conducted as a 52-week, open-label extension study of the antecedent double-blind study (ACP-103-069) to determine the long-term safety and tolerability of pimavanserin for the treatment of irritability associated with ASD in children and adolescents (5 through 17

years old at the time of enrolling into the antecedent double-blind study). Approximately 60 global sites and approximately eight countries will participate in this study.

The study will have two periods:

- Open-label treatment period (52 weeks)
- Safety follow-up period (at least 30 days)

[figure not shown]
Subjects who have completed the antecedent double-blind study and who have shown no significant worsening of symptoms at the end of the study as evidenced by the CGI-I of irritability will be included in this long-term extension study.

All subjects will receive the “low dose” for their age group (10 mg/day for 5 through 12 years old, and 20 mg/day for 13 through 17 years old) for the first two weeks of the study. At the Week 2 visit, the dose may be increased to the “high dose” (20 mg/day for 5 through 12 years old, and 34 mg/day for 13 through 17 years old) based on the Investigator’s assessment of clinical response. After the Week 2 visit and up to and including the Week 20 visit, dose adjustments, either increases or decreases, may be made at any clinic visit (scheduled or unscheduled), based on the Investigator’s assessment of clinical response and tolerability.

During the treatment period, clinic visits will be conducted at Baseline, and Weeks 2, 6, 12, 20, 28, 36, 44, and 52, or upon early termination (ET) from the study. In addition to the visit performed at time of study completion or premature discontinuation, a follow-up safety assessment will be conducted by telephone call at approximately 4 weeks after the last dose of study drug.

The study design schematic is provided in [Figure 1](#).

Figure 1 Schematic of Study Design

Abbreviations: EOT=end of treatment; ET=early termination; yrs=years

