3.5 Determination of Sample Size

The planned sample size for this study is not based on statistical power but will depend on the number of subjects who complete the antecedent double-blind study, and who rollover into this open-label extension study.

Assuming a drop-out rate of 15% in the antecedent study, it is estimated that approximately 193 subjects will be eligible to enroll in this OLE. Assuming all 193 subjects do enroll, then according to the Rule of Three, the 95% confidence interval for the occurrence rate of an unobserved adverse event is estimated as (0, 1.6%).

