14 SAFETY ANALYSES

The safety analysis will be performed on the Safety Analysis Set using descriptive statistics. No formal statistical testing will be performed for any of the safety endpoints.

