14.1 Adverse Events

All adverse events (AEs) will be coded using MedDRA version 24.0 or higher.

An AE (classified by preferred term) will be considered a treatment-emergent AE (TEAE) if it starts after the first study dose administration and no later than last study dose date + 30 days. AEs reported on Day 1 based on Baseline (pre-dose) findings (e.g. clinically significantly abnormal vital signs, laboratory test results, or electrocardiogram parameters) will not be considered as TEAEs.

The event counts and the number and percentage of subjects reporting TEAEs will be tabulated by SOC and preferred term; and, by SOC, preferred term, and maximum severity. If more than one AE occurs with the same preferred term for the same subject, the subject will be counted only once for that preferred term using the most severe and more related occurrence for the summarization by severity and by relationship to study drug, respectively.

The event counts and the number and percentage of subjects with any TEAEs will also be tabulated by preferred term without SOCs.

The incidence of most frequently reported (preferred terms reported by $\geq 5\%$ of subjects) TEAEs, TEAEs leading to discontinuation, TEAEs related to study drug, TEAEs by maximum severity, fatal TEAEs (i.e., events that cause death), serious TEAEs, and serious TEAEs related to study drug, will be summarized by SOC and preferred term.

The relationship of selected AEs to COVID-19 will be assessed as detailed in the GSD and provided in a listing.

An AE listing by subject will display all events, including those which are not treatment-emergent, and will include the verbatim term in addition to the MedDRA SOC and preferred term. Separate listings will be provided for TEAEs leading to discontinuation, TEAEs related to study drug, SAEs and fatal AEs.

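### No safety summary, including TEAEs and QTcF, is specified by dosing age group or open-label dose, so an age-specific signal could be diluted in the planned tables

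*SAP*

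**What the plan says.** Safety is the primary objective and TEAEs are the primary endpoint (Protocol 2.1.1 and 9.5.1). Everything is descriptive: "No formal statistical testing will be performed for any of the safety endpoints" (SAP 14).

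Dosing follows the age stratum carried over from the antecedent study. The starting dose is "10 mg/day for 5 through 12 years old, and 20 mg/day for 13 through 17 years old" (SAP 3.1), and the dose may be raised to 20 mg and 34 mg respectively. Thus 20 mg is the high dose in one stratum and the low dose in the other.

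On splitting the results:

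- Protocol 9.5.5 leaves subgroups to the SAP.
- SAP 12.5, the only section headed as a subgroup analysis, reads "Summaries of the change from Baseline in the ABC-I subscale scores will be presented by subgroups below". Age group is on its list.
- SAP 14.1: "The event counts and the number and percentage of subjects reporting TEAEs will be tabulated by SOC and preferred term". Severity and relationship to study drug are added. Age group, dose and cohort are not mentioned.
- SAP 14.4 gives QTcF categories by visit and for the overall post-baseline maximum.
- SAP 10.1.1 summarises highest, lowest and last dose level, but as exposure only.
- Many laboratory, vital-sign, ECG, physical-examination and C-SSRS summaries in Section 14 refer to a cohort. The only description of cohorts is in SAP 13.1, where they rest on the double-blind treatment group.

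**The concern.** The protocol itself names age and dose as possible modifiers of risk. Section 1.5.1 states that "pimavanserin dose-related QTc prolongation, and a trend for higher exposure with decreasing age and decreasing body weight, have been observed", in adolescents who were also taking other psychotropics. Section 1.4.2 reports simulated peak concentrations at 34 mg that rise as age and weight fall, and it sets lower doses for ages 5 to 12 for that reason. Section 6.4 lists QTc prolongation, weight gain and somnolence for active monitoring.

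A pooled TEAE or QTcF percentage averages two populations on different mg doses. If one of them carries most of the risk, the pooled figure understates it, and the planned summary tables would not show which group the events came from. The age stratum is already defined and already applied to ABC-I, but not to the endpoint that the study exists to describe.

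**Working it through.** **1. The plan's own precision figure.** SAP 3.5 states that "it is estimated that approximately 193 subjects will be eligible to enroll in this OLE" and quotes an upper 95% bound of 1.6% for an event that is never observed. Rule of Three: 3/193 = 1.55%, which rounds to 1.6%. It reproduces, but it is a pooled figure.

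**2. The same bound per age group.** The documents give no age split, so the shares are assumptions.

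| Share of 193 | n | 3/n |
|---|---|---|
| 30% | 58 | 5.2% |
| 50% | 96 | 3.1% |
| 70% | 135 | 2.2% |

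**3. Dilution and the 5% cut.** SAP 14.1 has a separate table for preferred terms reported by at least 5% of subjects. Pooled, that means at least 10 of 193 (0.05 × 193 = 9.65). Within groups of 58, 96 and 135 it means at least 3, 5 and 7.

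Let n1 subjects have true rate p1 and the other 193 − n1 have rate p0. The pooled rate is [n1·p1 + (193 − n1)·p0]/193. For n1 = 96, p1 = 8%, p0 = 1% this is (7.68 + 0.97)/193 = 4.5%. The chance of reaching the pooled cut is the upper tail of the sum of two independent binomials. The chance within the group is a single binomial tail. All rates are assumed.

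| n1 | p1 vs p0 | Pooled rate | Chance pooled ≥5% | Chance ≥5% within the group |
|---|---|---|---|---|
| 58 | 10% vs 2% | 4.4% | 34.4% | 93.8% |
| 96 | 10% vs 2% | 6.0% | 72.6% | 96.9% |
| 135 | 10% vs 2% | 7.6% | 92.8% | 98.5% |
| 58 | 8% vs 1% | 3.1% | 7.6% | 85.3% |
| 96 | 8% vs 1% | 4.5% | 36.5% | 89.1% |
| 135 | 8% vs 1% | 5.9% | 70.9% | 92.2% |

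Dilution is strongest when the affected group is the smaller one.

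**4. The cost of cutting within group.** A term at a true 2% in everyone reaches 5% by chance with probability 0.6% pooled. Within groups of 58, 96 and 135 the probability is 11.0%, 4.4% and 1.9%. Within-group columns are noisier, which is why the pooled column should stay.

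**5. Does cohort fill the gap?** On the SAP 13.1 description, a cohort contains both age groups. Every subject starts the extension on the low dose for the age group, and doses may be adjusted up to Week 20. Cohort therefore represents neither age group nor extension dose, and SAP 14.1 does not mention it for TEAEs.

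**The case against.** A reader might infer that all safety results are fully pooled and that the SAP has no other splits. The documents do not support that. Many Section 14 summaries are by cohort. Hemoglobin, hematocrit and uric acid are shown by sex, as is Tanner staging. Laboratory PCI values are shown by Baseline status, and disposition by region. What stands is that none of these splits is by age group or open-label dose.

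A reader might also infer that such tables will never be produced. SAP 1 places table specifications in a separate document that is not available here, and by-subject listings are planned. The supportable claim is that the split is not pre-specified in these two documents.

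It can fairly be said that the age-specific doses were chosen by simulation so that 20 mg at ages 5 to 12 and 34 mg at ages 13 to 17 both approach adult exposure at 34 mg (Protocol 1.4.2). The double role of 20 mg is therefore deliberate, and a difference between age groups is less expected than the mg figures suggest. That weakens the expectation of a signal. It does not remove the reason to look, because the matching rests on simulation.

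The strongest objection concerns tables by dose. All subjects spend the first two weeks on the low dose, so early events fall there by design. Later dose follows response and tolerability (Protocol 5.1.3.1). Half-lives of 57 hours for the parent drug and 200 hours for the metabolite (Protocol 1.3.2) carry exposure across a dose change. This objection stands: the age-group split should lead, and any dose split should be secondary.

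Finally, SAP 12.5 sits under efficacy, so its silence on safety is not itself an error, and Protocol 9.5.5 only says that subgroup analyses may be done. Nothing is contradicted. The gap lies in Section 14.

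**Conclusion.** The point holds as a gap in pre-specification. The plan has a defined age stratum that determines dose and a stated reason to suspect that risk varies with age and dose, but it specifies no safety summary by either.

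The size is illustrative, because the age split and the event rates are assumptions. For 10% vs 2%, the chance of reaching the 5% table falls from 94% within the group to 34% pooled when the affected group is 30% of subjects, but only from 98.5% to 93% when it is 70%. Missing that table does not hide an event, since SAP 14.1 also tabulates all TEAEs without a cut. What is lost is prominence and the link to an age group.

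Two stronger readings go too far. One treats QTcF, weight and laboratory results as primary. Only TEAEs are the primary endpoint, and the others are further safety analyses under the primary objective. The other takes the documents to show that an age-related risk exists. They show reasons to look: the reported QTc finding came from adolescents on combination treatment.

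This should be changed, but it does not invalidate the planned analysis.

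**What to change.** In SAP 14.1, 14.3 and 14.4, add columns for the two age groups as stratified in the antecedent study, beside the pooled column, for:

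- the TEAE overview, serious TEAEs and TEAEs leading to discontinuation;
- TEAEs in at least 5% of subjects, with the cut applied both overall and within age group;
- QTcF categories and change from Baseline;
- change in weight and BMI.

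Use the stratum rather than current age, because subjects keep their stratum, and with it their dose range, throughout the extension (Protocol 3.1.1).

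Define cohort for Section 14 and state whether it applies to the TEAE tables.

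Any summary by dose should be made within age group, since a split by mg alone would mix the two groups at 20 mg. It should be secondary, use exposure time on each dose as the denominator, and be labelled as non-randomised and open to time-on-study and carry-over confounding.

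The cost is SAP wording and extra table columns, with no new data. The downside is smaller cells: a Rule-of-Three bound of about 3.1% per age group at an assumed 50:50 split (2.2% to 5.2% over shares of 70% to 30%), against 1.6% pooled, and more chance entries in the within-group 5% list. That wider bound should be stated beside the pooled one in SAP 3.5.

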13 METHODS OF EFFICACY ANALYSES

13.1 Analysis of Continuous Efficacy Endpoints

Descriptive statistics for all secondary and exploratory efficacy endpoints listed in Section 12.1 will be tabulated by cohorts based on the double-blind treatment group at scheduled timepoints.

13.2 Categorical Analyses

At any given visit, the proportion of responders will be calculated using observed cases, i.e., number of responders divided by the number of subjects with non-missing assessment.

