### **9.5.3 Secondary Endpoint and Analysis**

The secondary endpoint in this study is the proportion of subjects who have at least 25% reduction from the antecedent study Baseline in the ABC-Irritability (ABC-I) subscale score AND a CGI-I of irritability score of 1 (very much improved) or 2 (much improved) compared to the antecedent study baseline status at Week 52.

The number and percentage of subjects who have at least 25% reduction from antecedent-study Baseline in the ABC Irritability (ABC-I) subscale score AND a CGI-I of irritability score of 1 (very much improved) or 2 (much improved) compared to the antecedent study baseline status will be tabulated by timepoint.

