5.2.1 Aberrant Behavior Checklist

The Aberrant Behavior Checklist (ABC) is a parent/caregiver-rated scale comprised of five empirically-derived subscales encompassing 58 items that describe various behavior problems ([Aman et al. 1985](#); [Kaat et al. 2014](#)). The subscales have been labeled as follows:

- I. Irritability (irritability, agitation, and crying): Items 2, 4, 8, 10, 14, 19, 25, 29, 34, 36, 41, 47, 50, 52, and 57 (15 items)
- II. Lethargy (lethargy and social withdrawal): Items 3, 5, 12, 16, 20, 23, 26, 30, 32, 37, 40, 42, 43, 53, 55, and 58 (16 items)
- III. Stereotypic Behavior: Items 6, 11, 17, 27, 35, 45, and 49 (7 items)
- IV. Hyperactivity (hyperactivity and noncompliance): Items 1, 7, 13, 15, 18, 21, 24, 28, 31, 38, 39, 44, 48, 51, 54, and 56 (16 items)
- V. Inappropriate Speech: Items 9, 22, 33, and 46 (4 items)

The ABC will be administered at Baseline and at all post-baseline visits from (Week 2 through Week 52). Items are rated on a 4-point Likert scale ranging from 0 (not at all a problem) to 3 (the problem is severe), with higher scores indicating more severe problems. Subscale scores are calculated by summing the items within that subscale.

Missing ABC item scores will not be imputed. If any item is missing within a subscale, then that particular subscale score will be missing.

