5.2.3 CGI-I

The CGI-I is a clinician-rated, 7-point scale that is designed to assess how much the subject's illness, in this study irritability associated with ASD, has improved or worsened relative to a baseline state at the beginning of the intervention ([Guy 1976](#)). The CGI-I of irritability will be administered at Baseline and at all post-baseline visits from (Week 2 through Week 52). The

possible scores are 1=very much improved, 2=much improved, 3=minimally improved, 4=no change, 5=minimally worse, 6=much worse, 7=very much worse.

Missing CGI-I of irritability scores will not be imputed.

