5.3.3 Unscheduled Assessments

Both scheduled and unscheduled assessments, including early termination visits, will be considered for planned timepoint analyses based on the above analysis visit windowing rules. All assessments will be presented in data listings.

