5.3.4 Multiple Measurements within Visit Windows

If multiple non-missing continuous measurements exist in an analysis window, the measurements will be selected based on the following rules if a single value is needed:

- For Baseline visit, the assessment closest to and prior to the time of the first dose of open-label study drug, whether scheduled or unscheduled, will be used as the baseline value. If multiple measurements occur on the same day at the same time or the time is not available, the one with later nominal visit (scheduled visits take precedence over unscheduled visit) will be selected.
- For post-baseline visits, the assessment closest to the target study day will be selected for the by-visit analyses. In these analyses, if two assessments are equidistant from the target day then the chronologically last assessment will be used. If multiple assessments have the same date/time, the one with later nominal visit (scheduled visits take precedence over unscheduled visit) will be selected.

If multiple non-missing categorical measurements exist in an analysis window, the measurements will be selected based on the following rules if a single value is needed:

- For Baseline visit, the assessment closest to and prior to the time of the first dose of open-label study drug, whether scheduled or unscheduled, will be used as the baseline value. If multiple measurements occur on the same day at the same time or the time is not available, the value with the lowest severity will be selected.
- For post-baseline visits, the assessment closest to the target study day will be selected for the by-visit analyses. In these analyses, if two assessments are equidistant from the target day then the chronologically last assessment will be used. Exceptions may be made for incomplete assessments, in which case, more complete assessments may be given priority. If multiple measurements occur on the same day, the value with the highest severity will be selected.

For safety analysis where the most extreme values should be selected (e.g. overall post-baseline minimum, overall post-baseline maximum, and potentially clinically important values), all non-missing post-baseline values should be considered, regardless of whether the value is selected for the by-visit summaries. All results will be presented in data listings.

When ECG is collected in triplicate, the average of the triplicate will be considered as one assessment for the analyses.

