5.4 Missing Data

In general, missing data will not be imputed unless otherwise specified in this document.

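### The Week 52 composite responder rate, the only secondary endpoint, is planned on observed cases only, with no rate over all treated subjects beside it

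*SAP*

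**What the plan says.** The composite requires an ABC-I score at least 25% below its value at the start of the double-blind study, together with a CGI-I of 1 or 2, at Week 52. It is the only secondary endpoint (Protocol 2.2.1 and 9.5.3; SAP 12.1).

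- **Denominator.** SAP 13.2: "the proportion of responders will be calculated using observed cases, i.e., number of responders divided by the number of subjects with non-missing assessment".
- **Windows.** SAP Table 2 opens the Week 52 window at study Day 337. SAP 5.3.3 adds: "Both scheduled and unscheduled assessments, including early termination visits, will be considered for planned timepoint analyses based on the above analysis visit windowing rules".
- **Missing data.** The protocol synopsis leaves this to the SAP. SAP 5.4: "In general, missing data will not be imputed unless otherwise specified in this document". SAP 5.2.3: "Missing CGI-I of irritability scores will not be imputed". SAP 5.2.1, on the ABC: "If any item is missing within a subscale, then that particular subscale score will be missing". SAP 12.3 says of derived scores that those "that are missing after the imputation of individual missing items (if any) will not be imputed".
- **Population.** SAP 4 assigns every analysis to the Safety Analysis Set, meaning subjects with at least one open-label dose.
- **Tabulation.** Protocol 9.5.3 plans the composite at each timepoint, beginning "The number and percentage of subjects who have at least 25% reduction from antecedent-study Baseline in the ABC Irritability (ABC-I) subscale score", and gives no denominator. SAP 13.1 tabulates the efficacy endpoints by double-blind treatment cohort.

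**The concern.** Taken together, these rules remove from the Week 52 rate anyone without ratings on or after Day 337. An early-termination rating before that day counts at an earlier visit. One on or after that day counts at Week 52, whenever drug was stopped.

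Departure can be tied to outcome. Protocol 4.5 lists lack of efficacy as a reason for discontinuation, and Protocol 4.8.2.1 withdraws subjects who need a prohibited medication. Such subjects bear directly on whether response continued, yet they are in neither the numerator nor the denominator. The percentage then describes those still rated at Week 52, not those who started open-label drug. If follow-up differs between the double-blind cohorts, their rates also describe differently selected subsets.

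A smaller gap concerns the two-part definition. SAP 13.2 does not say what a non-missing assessment is when only one component is available. A subject with CGI-I of 4 and one blank ABC-I item has no ABC-I score, but has already failed the composite. Two programmers could treat that subject differently.

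**Working it through.** **The plan's own figure.** Neither document states a responder rate. The only calculated figure is the Rule of Three limit in Protocol 9.3 and SAP 3.5. It reproduces (3/193 = 1.55%, rounded to 1.6%) but does not concern this endpoint.

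**Inputs**

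- N = 193, the approximate planned enrolment (Protocol 9.3, SAP 3.5).
- d = share of treated subjects without a Week 52 composite. This is not given. The range starts at 15%, the dropout assumed for the antecedent study. For context, the 26-week adult study in Protocol 1.3.1 had 85.9% completion, so 14.1% did not complete. The values 20%, 30% and 40% are assumptions.
- p = observed-case response rate. This is not given; 60% and 40% are assumed.
- q = response rate the unrated subjects would have had. This is unknown.

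**Formulas**

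All-treated rate = (1 − d)p + dq.

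Bias of the observed-case rate as a statement about all treated subjects = p − [(1 − d)p + dq] = d(p − q). It is positive if q < p, zero if q = p, and negative if q > p.

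**Results**

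| Quantity | d = 15% | d = 20% | d = 30% | d = 40% |
|---|---|---|---|---|
| p = 60%: lower bound (q = 0) | 51% | 48% | 42% | 36% |
| p = 60%: largest overstatement, points | 9 | 12 | 18 | 24 |
| p = 60%: overstatement if q = 30%, points | 4.5 | 6 | 9 | 12 |
| p = 60%: upper bound (q = 1) | 66% | 68% | 72% | 76% |
| p = 60%: largest understatement, points | 6 | 8 | 12 | 16 |
| p = 40%: lower bound (q = 0) | 34% | 32% | 28% | 24% |
| p = 40%: upper bound (q = 1) | 49% | 52% | 58% | 64% |

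**In whole subjects, N = 193, p about 60%**

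- d = 15%: 164 rated, 98 responders. Observed 98/164 = 59.8%; lower bound 98/193 = 50.8%; upper bound (98 + 29)/193 = 127/193 = 65.8%.
- d = 30%: 135 rated, 81 responders. Observed 81/135 = 60.0%; lower bound 81/193 = 42.0%; upper bound (81 + 58)/193 = 139/193 = 72.0%.

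**Component rule.** Suppose responder status can be settled for 135 subjects, and 5 of them (an invented number) are settled only because they fail one component while the other is missing. Counting them gives 81/135 = 60.0%. Excluding them gives 81/130 = 62.3%. The all-treated lower bound is 81/193 either way.

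**The case against.** Observed cases is a stated choice and contradicts nothing. The study is descriptive, adverse events are primary, and no test depends on this rate. A rate among those still assessed is one reasonable reading of continued response to long-term treatment. Attrition will be visible, because the SAP plans discontinuations by reason, exposure categories and Kaplan-Meier curves of time on drug. The responder count and the Safety Analysis Set size are both planned, so a reader could divide one by the other. Table specifications are in a separate document that was not available. The magnitudes are assumed. Counting every unrated subject as a non-responder also penalises departures unrelated to efficacy, such as pregnancy or sponsor termination.

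Most of this stands as a limit on weight. The bias can go either way, and no overstatement has been shown. But disposition and exposure outputs do not give a responder rate over all treated subjects, and a number that a reader could derive is not a planned, labelled result. The Safety Analysis Set rule fixes the population; SAP 13.2 then narrows the denominator within it. The harshness of the added rate is a reason to label it a lower bound, not to omit it.

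On the component gap, SAP 5.3.4 says "Exceptions may be made for incomplete assessments, in which case, more complete assessments may be given priority". That sentence sits under the rules for categorical measurements. For continuous scores the selection is already among non-missing values. Both rules reduce the number of half-missing composites, but neither says how to count those that remain.

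**Conclusion.** The concern holds. The sole secondary endpoint has one planned denominator, subjects with a non-missing assessment at Week 52, and neither the protocol nor the SAP plans the all-treated counterpart. At an assumed 60% observed rate with 15% to 40% of subjects unrated, the observed rate could exceed the all-treated rate by up to 9 to 24 points or fall below it by up to 6 to 16 points. If the unrated respond half as often, it overstates by 4.5 to 12 points; if equally often, by nothing. These sizes rest entirely on assumed dropout and response rates. No error rate or decision rule is affected; what is at stake is the interpretation of one descriptive percentage. The conclusion is limited to the protocol and SAP, since the table specifications were not available.

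**What to change.** In SAP 13.2, keep the observed-case rate and add two sentences:

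1. Overall and by the double-blind treatment cohorts of SAP 13.1, also report Week 52 responders divided by all Safety Analysis Set subjects, counting those without a composite in the Week 52 window as non-responders. Label this a lower bound and show both denominators.
2. A subject who fails either observed component is a non-responder even if the other component is missing.

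The cost is one added table row per cohort, from data already collected. The added rate is conservative where dropout is unrelated to efficacy, which is why it needs the lower-bound label.
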